6.3.1 Analysis of Secondary Outcome of Interest

One secondary outcome of interest is LV function quantified as EF and SF over the courses of therapy and post-treatment follow-up. LVEF and LVSF trajectories will be determined by group-based latent trajectory modeling, a type of structural equation modeling which identifies distinct clusters of individuals based on development, progression, and resolution patterns pertaining to the repeated measures of a given variable. The following factors will be explored as predictors identified trajectory phenotypes: age, gender, race, ethnicity, weight group, presenting white blood cell count, and baseline EF/SF. Univariate and

multivariable mixed effects regression models will be fitted to quantify the association between bacteremia and longitudinal EF and SF measurements.

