2.2 Secondary Objectives

2.2.1 Identify subpopulations based on distinct longitudinal patterns of LV ejection fraction (EF) and fractional shortening (SF) decrease and recovery and evaluate the impact of bacteremia on the longitudinal patterns of LVEF and LVSF. Compare relapse risk (RR) and OS in subgroups.

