3.3 Total Number of Study Sites/Total Number of Subjects Projected

3.3.1 Duration of Study Participation

No direct patient contact is necessary for this study; only medical record abstraction. The chart abstraction window for each participant will include the time period from the start of the first course of chemotherapy until the date of last patient contact or death.

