3.4 Study Population

The study population will include all AML and MDS patients who received or will receive chemotherapy starting January 1, 2012 at any of the seventeen participating pediatric institutions across the US. Patients discharged within 3 days after completion of that chemotherapy course will be categorized as 'early discharge' to outpatient management during neutropenia. Patients meeting eligibility criteria for 'early discharge' but remaining in the hospital more than 3 days after completion of that chemotherapy course will be categorized as inpatient management. Patients will be considered early discharge-eligible if there is no evidence of fever, infection or intensive care unit (ICU) level care within \pm 3 days of the last dose of chemotherapy.

3.4.1Aim 1 Inclusion Criteria

- 1) Males or females less than 19 years of age at initial AML/MDS diagnosis.
- 2) Receipt or planned receipt of standard intensive AML frontline chemotherapy any time from January 1, 2012 or after.

3.4.2Aim 1 Exclusion Criteria

- Patients being treated for relapsed AML
- Patients with Acute Promyelocytic Leukemia (APML)
- Patients undergoing stem cell transplant (SCT)
- Patients receiving reduced intensity frontline chemotherapy

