5 STUDY EVALUATIONS AND MEASUREMENTS

5.1 Screening and Monitoring Evaluations and Measurements

5.1.1 Medical Record Review

The following variables will be abstracted from the medical chart:

Variable Date of birth Sex Patient race/ethnicity Date of AML/MDS diagnosis Age at AML/MDS diagnosis Vital status Date of death or date of last known follow-up Location of death (in hospital or at home) AML subtype AML risk classification and cytogenetics Hospital admission start/stop dates Chemotherapy course Chemotherapy regimen and start/stop dates Course start/stop dates Clinical trial enrollment and specific protocol Documentation of deviation from planned chemotherapy course Presence/type of central line MRD post courses and dates of MRD obtained Post course remission status Daily max. fever; how was temperature taken Infections during chemotherapy courses ICU care during chemotherapy courses ANC measurements post chemotherapy Dates of ANC measurements Dates and results of microbiological cultures/PCRs onset during post chemotherapy course follow-up Mucositis by course Systematic antimicrobial prophylaxis at each course Height, weight, and body surface area at start of chemotherapy course Nutritional status/supplemental support requirements on day of chemotherapy completion Ability to practice oral hygiene Insurance status at course start (private, self-pay, public, other) English spoken? Home address Availability of working telephone Automobile/taxi voucher requirements Date of relapse Site of relapse Date of transplant Type of transplant Echocardiographic evaluations (e.g., dates, resulting measurements, measurement mode) Blood pressure and heart rate at echocardiographic evaluations Dexrazoxane administration Malignant blast percentage

| Bone marrow malignant blast percent |
|---|
| Empiric/definitive anti-infective use |
| Preferred language |
| Treatment and positive blood cultures at outside hospital (y/n) |
| Down Syndrome diagnosis |
| CNS status at the end of each course |
| Outpatient encounters (e.g., clinic/day hospital, ED) |

Some information will be retained for all screened patients to document the reasons for ineligibility. Specifically, we will be retaining information on age, leukemia diagnosis, treatment course, and whether the patient received reduced intensity chemotherapy.

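### The EF/SF series has no stop at relapse, so echocardiograms taken after relapse can help define the trajectory groups that are then compared on relapse risk

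*Combined protocol and SAP*

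**What the plan says.** - **Measurement window.** Section 6.3.1 on the secondary outcome states: "One secondary outcome of interest is LV function quantified as EF and SF over the courses of therapy and post-treatment follow-up". No end date or ending event is given.
- **Abstraction window.** Section 3.3.1: the chart window "will include the time period from the start of the first course of chemotherapy until the date of last patient contact or death".
- **Forming the groups.** Section 6.3.1 (secondary): "LVEF and LVSF trajectories will be determined by group-based latent trajectory modeling". The groups come from the repeated measures, and no landmark is stated.
- **Use of the groups.** Section 2.2.1: "Compare relapse risk (RR) and OS in subgroups".
- **Bacteremia model.** Section 6.3.1 (secondary): "multivariable mixed effects regression models will be fitted to quantify the association between bacteremia and longitudinal EF and SF measurements". No time limit is stated.
- **Dates available.** Section 5.1.1 lists "Date of relapse Site of relapse Date of transplant Type of transplant Echocardiographic evaluations (e.g., dates, resulting measurements, measurement mode", and also chemotherapy regimen with start and stop dates. The start of transplant conditioning is not a listed variable.
- **Exclusions.** Section 3.4.2 lists "Patients being treated for relapsed AML" and patients undergoing stem cell transplant, without a time point. The table of contents says under the same section number that there are no exclusion criteria.

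**The concern.** Section 1.2 gives the motive for this objective: how patterns of cardiac function bear on later cardiomyopathy and treatment outcome. For that question the pattern has to come before the outcome. With an open series, a child who relapses goes on contributing EF/SF values during and after further treatment. If that treatment lowers EF, the child's class is partly a consequence of the relapse, and the class is then compared on relapse risk. A larger sample or more covariates would not remove this, because the grouping variable itself carries the outcome. At stake is a reported link between EF decline and relapse, in the only listed secondary objective, that could be produced by the measurement window alone.

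**Working it through.** The plan gives no sample size, relapse rate or EF effect for this objective, so there is no figure of its own to reproduce. The check is a reading of the text followed by an illustration.

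**Step 1: does any text stop the series?** Sections 2.2.1, 3.3.1, 3.4, 5.1.1 and both parts headed 6.3.1 contain no stop at relapse, salvage therapy or transplant. By contrast, the bacteremia endpoint in Section 6.1 has an explicit start and end. The exclusion of patients being treated for relapse cannot mean dropping everyone who relapses later, because relapse is an outcome in Section 2.2.1 and its date and site are abstracted.

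**Step 2: size by arithmetic.** All inputs are assumptions: relapse r = 0.35, true decline class c = 0.10 and independent of relapse, and a share d of the other relapsed children moved into the decline class by EF falls after relapse.

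- Decline class, relapsed: r × (c + (1 − c)d)
- Decline class, not relapsed: (1 − r) × c = 0.65 × 0.10 = 0.065
- Other class, relapsed: r × (1 − c)(1 − d)
- Other class, not relapsed: 0.65 × 0.90 = 0.585

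| d | Relapse risk, decline class | Relapse risk, other class |
|---|---|---|
| 0 | 0.035 / 0.100 = 35.0% | 0.315 / 0.900 = 35.0% |
| 0.10 | 0.0665 / 0.1315 = 50.6% | 0.2835 / 0.8685 = 32.6% |
| 0.30 | 0.1295 / 0.1945 = 66.6% | 0.2205 / 0.8055 = 27.4% |

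Here d is itself the misclassification, so the table shows what a given d does and not how large d is.

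**Step 3: does a trajectory model produce such a shift?** A two-class model with quadratic class means was fitted to simulated data: n = 540 (Section 6.4), 10 echocardiograms per child, a true low-EF class of 20% unrelated to relapse, and relapse falling between the 5th and 9th echocardiogram. Everything except n is assumed. There were 200 replicates at 20% relapse and 150 at 40%.

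| Relapse | EF fall after relapse (points) | Open series: low-EF vs other class | False positives at nominal 5% |
|---|---|---|---|
| 20% | 0 | 0.20 vs 0.20 | 6% |
| 20% | 3 | 0.28 vs 0.16 | 86% |
| 20% | 6 | 0.37 vs 0.12 | 100% |
| 20% | 9 | 0.46 vs 0.07 | 100% |
| 40% | 0 | 0.41 vs 0.40 | 4% |
| 40% | 3 | 0.51 vs 0.35 | 95% |
| 40% | 6 | 0.63 vs 0.27 | 100% |

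With the series stopped at relapse, the two classes had equal relapse in every setting (0.20 vs 0.20 and 0.40 vs 0.40), with 3% to 7% false positives. The echocardiograms after relapse are therefore the source. In this layout the true low-EF class shows itself before any relapse occurs, so the simulation does not test the separate problem that stopping makes series length depend on the outcome.

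**Step 4: bacteremia model.** Spurious EF difference = (difference in relapse proportion by bacteremia status) × (share of a relapsed child's echocardiograms taken after relapse) × (EF fall). With an assumed share of 0.35:

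- no difference in relapse: 0
- 5 percentage points, 3-point fall: 0.05 × 0.35 × 3 = 0.05 EF points
- 20 percentage points, 9-point fall: 0.20 × 0.35 × 9 = 0.63 EF points

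**The case against.** The strongest reply is that the plan is silent rather than wrong. The window in Section 3.3.1 governs abstraction, which relapse and OS need in any case. It does not say that every echocardiogram enters the model. The study concerns frontline chemotherapy, so the courses of therapy in Section 6.3.1 are naturally read as frontline courses. Follow-up after treatment is included on purpose, because recovery and later cardiomyopathy are of interest, and a blanket cut would work against that.

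Much of this stands. A reader might infer that the plan chooses to use measurements taken after salvage therapy. It does not say so; they enter by default under the written windows. A reader might also take Section 2.2.1 to concern frontline cardiotoxicity alone, but its text sets no such limit, which is why the full series should be kept for description. The reply does not rescue the relapse comparison, however, because an analyst following the text has no instruction to leave these values out.

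Two extensions are tempting and are not supported:

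- **Transplant.** A transplant without prior relapse is not a consequence of relapse, so the circularity argument does not reach it. Section 3.4.2 can also be read as removing these patients.
- **Bacteremia model.** The distortion is zero if bacteremia and relapse are unrelated, and the documents suggest no such relation.

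It is also fair to object that stopping at relapse is not a complete remedy, since it ties series length to the outcome. That is correct, and the fix allows for it.

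**Conclusion.** The concern holds for the comparison of trajectory groups on relapse risk. As written, values after relapse can help define groups that are then compared on relapse, and an association can appear where none exists. This is conditional on treatment after relapse lowering EF; without such a fall there is no distortion. Under the assumptions shown, a true 35% in both groups reads as 51% versus 33% up to 67% versus 27%, and in the simulation a 3-point fall was enough for 86% to 95% false positives. The relapse rates, class sizes and EF falls are all assumed, so these figures give direction and plausible scale, not a forecast. For the bacteremia model the effect is at most about 0.6 EF points over the range examined, and it needs relapse to differ by bacteremia status. For transplant, the documents support only a request to reconcile the passages. The plan should be changed, but the matter concerns a secondary objective and leaves the two primary endpoints untouched.

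**What to change.** In Section 6.3.1 (secondary):

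1. For the trajectory groups compared on relapse risk and OS, use only EF/SF measurements taken before the earlier of relapse or start of non-frontline therapy.
2. Make that comparison from a stated landmark, for example the end of frontline therapy, among patients alive and relapse-free at that point, with groups formed from measurements up to it. Alternatively, specify a joint model. Stopping at relapse alone is not enough.
3. Keep the full series to last contact as a labelled descriptive or sensitivity analysis of recovery and later cardiomyopathy.
4. For the bacteremia mixed model, apply the same stop as a sensitivity analysis.
5. Reconcile the transplant exclusion in Section 3.4.2 with the table of contents entry and with the abstraction of transplant date in Section 5.1.1. If transplanted patients remain in the cohort, use the collected transplant date in a sensitivity analysis, since conditioning start is not listed.

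The cost is a few sentences and a filter on relapse, regimen and echocardiogram dates already listed for abstraction; regimens would need to be marked as frontline or not. The price in information is fewer late echocardiograms in the compared groups, and children who relapse before the landmark drop out of that comparison.

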In order to appropriately inform the decision for outpatient versus inpatient management of neutropenia associated with pediatric AML chemotherapy, a comprehensive study that collects pertinent clinical outcomes is necessary. Given that infectious complications are the leading cause of treatment related mortality among AML patients (22) and among MDS patients (24, 25), identifying such a neutropenia management strategy that leads to the best clinical outcomes will have a substantial impact on care of these patients.

Bacteremia, a cause of transient cardiac decline, occurs frequently during AML treatment and contributes to the development of cardiac dysfunction.(26) COG guidelines for rechallenging patients to anthracycline chemotherapy distinguish infection-associated LV systolic dysfunction (LVSD) from LVSD not associated with infection, allowing patients who experience resolution of infection-associated LVSD to receive additional anthracycline therapy. However, there are no data comparing the longitudinal trajectories of EF/SF or the impacts on subsequent cardiomyopathy and treatment outcomes for these distinct presentations of cardiotoxicity.

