4 STUDY PROCEDURES

4.1 Aim 1

The only study procedure for this cohort is chart abstraction; thus, there will be no study visits or other patient contact encounters required from the participant.

4.1.1 Retrospective Patient Identification:

Local study investigators (pediatric oncologists and study coordinators) at each of the seventeen participating pediatric institutions will review their hospital AML or MDS registry to identify patients from January 1, 2012 through the date of IRB approval that meet enrollment criteria.

4.1.2 Prospective patient identification:

The prospective data abstraction timeline begins the date of IRB approval and lasts through the duration of the study. Study investigators at each institution will communicate on a weekly basis with their inpatient leukemia service to identify AML or MDS patients potentially eligible for study enrollment. Once identified, study personnel will review each patient for study eligibility criteria.

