4.2 Subject Completion/Withdrawal

This is an analysis of data that are documented in the course of providing clinical care to subjects. As there are no additional interventions necessary for the execution of this study and we do not foresee any adverse effects stemming from the research, a waiver of consent will be submitted to address the issue of subject withdrawal.

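### The EF/SF models pool routine-care echocardiograms without accounting for when or why they were done, so more frequent scanning during bacteremia could produce an association with decrease and recovery

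*Combined protocol and SAP*

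**What the plan says.** Objective 2.2.1 looks for subgroups with distinct patterns of EF/SF decrease and recovery, asks what impact bacteremia has on those patterns, and compares relapse risk and OS between subgroups.

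The data are whatever care produced. Section 4.1 says that "there will be no study visits or other patient contact encounters required from the participant", and section 4.2 says "This is an analysis of data that are documented in the course of providing clinical care to subjects". Section 5.1.1 lists "Echocardiographic evaluations (e.g., dates, resulting measurements, measurement mode" among the abstracted items. It names no scan indication, although the entry gives examples only. The abstraction window in section 3.3.1 runs "from the start of the first course of chemotherapy until the date of last patient contact or death".

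Section 6.3.1 (Analysis of Secondary Outcome of Interest) defines the outcome as "LV function quantified as EF and SF over the courses of therapy and post-treatment follow-up" and states that "LVEF and LVSF trajectories will be determined by group-based latent trajectory modeling". It adds that "multivariable mixed effects regression models will be fitted to quantify the association between bacteremia and longitudinal EF and SF measurements". It does not mention measurement windows, scheduled versus prompted scans, or whether bacteremia is time-varying. The propensity score in the primary-outcome part of 6.3 concerns inpatient versus outpatient management and does not bear on this objective.

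**The concern.** Section 1.2 states: "Bacteremia, a cause of transient cardiac decline, occurs frequently during AML treatment". The same section separates infection-associated LV dysfunction from other dysfunction and refers to its resolution. Labelling a decline as infection-associated requires a scan near the infection, and showing that it resolved requires another. Children with bacteremia may therefore have scans that capture both the dip and the recovery. A child without bacteremia who has an equally short dip, and recovers before the next scan, is recorded as stable.

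If that happens, the decrease-and-recovery group partly reflects who was scanned at the nadir. The bacteremia association would then mix any real effect with differential detection, and the relapse and OS comparisons would inherit the same grouping.

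**Working it through.** The plan gives no echocardiogram frequency, effect size or power for this objective, so there is no stated figure to reproduce. The check asks what the planned analysis would show if bacteremia had no effect on EF.

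**Inputs.** From the documents: 540 children (section 6.4). All else is assumed:
- 4 courses per child, with bacteremia in 25% of courses.
- A dip of D = 10 EF points in a fraction p of courses, the same with and without bacteremia.
- One routine echocardiogram before the next course, by which a fraction r = 0.1 of dips persist.
- An extra nadir scan with probability qb in bacteremic courses and q0 in others.
- Between-child and residual SD of 4 EF points each.

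**Formulas.**
- Courses in which decrease then recovery is seen: p × q × (1 − r). The ratio between groups is qb/q0, whatever p is.
- Approximate false difference in mean EF, all scans pooled with no timing term: −D × p × [(r + qb)/(1 + qb) − (r + q0)/(1 + q0)].

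**Worked case**, p = 0.10, qb = 0.30, q0 = 0.05. Pattern: 0.10 × 0.30 × 0.9 = 2.7% versus 0.10 × 0.05 × 0.9 = 0.45%. Mean: −10 × 0.10 × (0.40/1.30 − 0.15/1.05) = −(0.308 − 0.143) = −0.16.

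The simulations fitted a random-intercept model with cluster-robust SE, using 150 replicates (300 for the last two rows). Rejection is at a nominal 5%.

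| p | qb / q0 | Pattern seen (formula) | Mean difference, formula | Simulated | Rejection |
|---|---|---|---|---|---|
| 0 | 50% / 5% | 0 vs 0 | 0 | +0.02 | 3% |
| 10% | 30% / 30% | 2.7% vs 2.7% | 0 | −0.01 | 4% |
| 20% | 30% / 30% | 5.4% vs 5.4% | 0 | +0.03 | 10% |
| 10% | 30% / 5% | 2.7% vs 0.45% | −0.16 | −0.13 | 6% |
| 10% | 50% / 5% | 4.5% vs 0.45% | −0.26 | −0.20 | 15% |
| 20% | 30% / 5% | 5.4% vs 0.9% | −0.33 | −0.32 | 31% |
| 15% | 80% / 10% | 10.8% vs 1.35% | −0.48 | −0.50 | 65% |
| 15% | 60% / 30% | 8.1% vs 4.05% | −0.20 | −0.21 | not recorded |

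With 150 replicates the rejection rates are rough: √(0.15 × 0.85/150) = 0.029, about 3 percentage points.

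**Both conditions are needed.** With no dips from other causes, or with equal scanning, there is no systematic bias.

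**Adding a nadir/pre-course term.** When scanning depends on bacteremia only, a fraction p of nadir scans shows a dip in both groups, so the term removes the mean bias. The simulated coefficient was −0.01 in each of three cases: 80%/10% (rejection 5%), 50%/5% with p = 10% (5%) and 60%/30% (8%). When the dip itself prompted scans, −0.15 remained in one run. In general, if a dip raises the scan probability from u to t, the share of nadir scans showing a dip is p·t/(p·t + (1 − p)·u). The residual bias then depends on t/u in each group and can take either sign. The term does nothing for trajectory classification.

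**Restricting to routine pre-course scans.** With one such scan in every course, the coefficient was −0.03 to +0.05 and rejection 3% to 9%. The restriction must not fall back on whichever scan came last. If routine scans exist in only 70% of courses (p = 15%, 80%/10%), using the last available scan gives −10 × 0.15 × [(0.7 × 0.1 + 0.3 × 0.8)/(0.7 + 0.3 × 0.8) − (0.7 × 0.1 + 0.3 × 0.1)/(0.7 + 0.3 × 0.1)] = −1.5 × (0.330 − 0.137) = −0.29. The simulation gave −0.28 with 19% rejection.

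No latent trajectory model was fitted. The pattern columns show what such a model would be given, not the classes it would return.

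**The case against.** The strongest reply is that the documents nowhere say when or why scans were done. Trial enrollment is abstracted, so some scans may follow a treatment protocol's schedule. The pattern ratio only returns the assumed scan rates. The mean bias is small: at most 0.50/4 = 0.125 of the assumed residual SD in the cases tabulated. It disappears once scan timing is modelled, and the plan, which collects scan and course dates and calls its models multivariable, does not rule that out. Bacteremia is not among the listed predictors of trajectory group. Limiting the main analysis to pre-course scans would discard the transient declines that the objective is about.

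Most of this stands, and it limits the claim. It does not remove the point. The plan does not say that timing will be modelled. A timing term does not protect the trajectory groups or fully handle scans prompted by the dip. Objective 2.2.1 asks for the impact of bacteremia on the patterns themselves. The loss of transient dips is a reason to run the restricted analysis alongside the all-scan one rather than in its place.

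A reader might infer that dips are seen mainly in septic children, or that the objective cannot be answered. The documents support neither: they give no scan timing, and the bias requires two conditions that they do not establish. Nor do they show that an observed dip is spurious, since section 1.2 treats bacteremia as a real cause of decline.

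**Conclusion.** The point holds as a gap in the plan, not as a demonstrated bias. EF and SF come only from routine-care scans, and the trajectory and mixed models pool them with no rule for timing. If scanning at the nadir is more frequent with bacteremia, and short dips from other causes are missed without it, a null effect can appear as an association. Under the assumed rates the observed pattern differs by qb/q0, from 2-fold (60%/30%) to 10-fold (50%/5%). Mean EF shifts by −0.13 to −0.50 points, with false rejection from 6% to 65% where recorded. These figures illustrate the mechanism and do not predict the trial's result. Only a secondary objective is affected; the bacteremia and time-to-next-course comparisons are not.

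**What to change.** Amend the secondary-outcome part of section 6.3.1, using echocardiogram, course and culture dates already abstracted:

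1. In the mixed models, include scan timing within the course (nadir versus pre-course window) and treat bacteremia as time-varying.
2. Pre-specify a parallel trajectory and mixed-model analysis. Limit it to scans in a defined pre-course window and outside a defined interval around a positive culture, plus end of therapy and follow-up. Treat a course with no qualifying scan as missing; do not substitute the sepsis-time scan.
3. Report scan counts and timing per course by bacteremia status. This shows directly whether scanning differs.
4. Claim an impact of bacteremia on decrease-and-recovery patterns only if the two analyses agree. Otherwise describe an association open to differential detection.

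The cost is SAP wording and one further set of models. Recording the scan indication is optional; if it is not already captured, it means returning to charts from 2012 onward at seventeen sites. The drawback is that the restricted analysis speaks only to change that persists to the next course. A real effect that resolves sooner would not be confirmed by it, so the all-scan analysis is kept alongside.

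### Echocardiographic measurement mode is listed for abstraction, but the model that forms the EF/SF trajectory classes has no term or rule for mode or hospital

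*Combined protocol and SAP*

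**What the plan says.** Section 5.1.1 (Medical Record Review) includes the item "Echocardiographic evaluations (e.g., dates, resulting measurements, measurement mode", so mode is foreseen as data, although only as an example within a parenthesis.

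Section 6.3.1 (Analysis of Secondary Outcome of Interest) defines the outcome as "LV function quantified as EF and SF over the courses of therapy and post-treatment follow-up". It then says "LVEF and LVSF trajectories will be determined by group-based latent trajectory modeling", with clusters based on "development, progression, and resolution patterns pertaining to the repeated measures of a given variable". The factors to be explored as predictors of class are "age, gender, race, ethnicity, weight group, presenting white blood cell count, and baseline EF/SF": seven factors, with neither mode nor hospital among them. Separately, univariate and "multivariable mixed effects regression models will be fitted to quantify the association between bacteremia and longitudinal EF and SF measurements"; no covariates or random effects are named for these.

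Section 2.2 states what the classes are for: "Identify subpopulations based on distinct longitudinal patterns of LV ejection fraction (EF) and fractional shortening (SF) decrease and recovery", then "Compare relapse risk (RR) and OS in subgroups".

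The values come from routine-care records (section 4.2) at seventeen hospitals (section 3.3.2). No central reading or harmonisation of echocardiograms is described.

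**The concern.** Group-based trajectory modelling accounts for differences in level and shape by adding classes. A systematic difference between modes that has no term in the model is therefore a candidate class. Examining predictors of class membership afterwards does not undo this, and mode is not on that list in any case.

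Two routes matter. If some children are always measured by a lower-reading mode, or at a lower-reading hospital, the model can find a low-level class. If some children move to a lower-reading mode and stay on it, the model can find a declining class. In either case the subgroups compared for relapse risk and overall survival would partly sort children by how and where they were measured. The same offset could bias the estimated association of bacteremia with EF and SF, if mode use differs after bacteremia and the mixed model leaves mode out.

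**Working it through.** The plan gives no sample size, SD, number of echocardiograms or mode difference for the EF/SF analysis, so there is no stated figure to reproduce. What follows is illustrative.

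**1. Can an offset create a class?**

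- From the documents: n = 540 (section 6.4).
- Assumed: six echocardiograms per child; true EF constant at 62 for every child; residual SD 5 points; no between-child variation; 10% or 30% of children affected; offset of 0, 2, 4 or 6 points.
- Model: trajectory mixture, quadratic in time, common residual variance, one versus two classes chosen by BIC, 15 replicates per cell.

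Share of replicates in which BIC chose a false second class:

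| Pattern | Children affected | 2 points | 4 points | 6 points |
|---|---|---|---|---|
| Constant offset | 30% | 7% | 100% | 100% |
| Constant offset | 10% | 0% | 80% | 100% |
| Lasting switch midway | 30% | 0% | 73% | 100% |
| Lasting switch midway | 10% | 0% | 0% | 60% |
| Temporary switch | 30% | 0% | 0% | 53% |
| Temporary switch | 10% | 0% | 0% | 0% |

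With no offset the share was 0%. The precision is coarse: 73% is 11 of 15, with standard error √(0.733 × 0.267 / 15) = 0.11, and 0 of 15 has a one-sided 95% upper limit of 1 − 0.05^(1/15) = 0.18.

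A repeat with 30% affected and offsets of 4 to 5 points gave 100% for the constant offset and 50 to 100% for the lasting switch. The temporary switch gave 0% at 4 points and 25% at 5. A further run, allowing up to four classes, gave extra classes for the temporary switch in 1 of 12 replicates at 4 points and 1 of 12 at 5.

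**2. Does the remedy work?** In the repeat above, entering mode in the class-forming model brought the share of false classes to 0%.

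**3. What if children truly differ in level?** Assume between-child SD 4, within-child SD 5 and five echocardiograms. The SD of a child's mean EF is √(16 + 25/5) = 4.58. Comparing children always measured by one mode with children always measured by the other, AUC = Φ(offset / (4.58 × √2)):

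- offset 2: Φ(0.31) = 0.62
- offset 4: Φ(0.62) = 0.73
- offset 5: Φ(0.77) = 0.78

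So even where level classes would exist anyway, the offset tilts who falls into them.

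**4. Bacteremia association, if the mixed model omits mode.** Assume that 30% of echocardiograms after bacteremia and 10% of the others use the lower-reading mode. Bias = −offset × (0.30 − 0.10): −0.4 points at offset 2, −0.8 at 4, −1.0 at 5. With mode in the model, the −0.8 bias disappeared.

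**The case against.** - **Silence is not a decision.** A reader might infer that the plan has chosen to pool modes. It does not say so. Listing mode for abstraction fits equally well with an intention to select or adjust by mode. This stands: the gap is that no rule is written, not that a wrong rule is.
- **Mode may not be available throughout.** A reader might also infer that mode is recorded for every echocardiogram. Section 5.1.1 gives it only as an example item, and charts go back to 2012. This stands, and the remedy must allow for undocumented mode.
- **The mixed models may include mode.** The seven listed factors are predictors of trajectory class, not mixed-model covariates, so their content shows nothing about the mixed models. This stands: the bias in step 4 is conditional, and the gap is firm only for the trajectory model.
- **Hospital-level control is promised.** Section 6.2 says in general terms that analyses will control for hospital-level factors, and section 6.3.1 (Primary Outcomes) repeats this for the bacteremia analysis. This weakens the between-hospital part. But section 6.2 does not mention mode, and section 6.3.1 (Secondary Outcome) does not carry the promise into the formation of classes.
- **A false fall and rebound is tempting but weakly supported.** One might picture a child imaged by a different mode while ill, giving an apparent decline and recovery. No section mentions such a practice, and temporary switches of 4 to 5 points seldom produced a class. A constant offset produces a level class, not a decline.
- **Level classes arise anyway.** With between-child SD 4 and no offset at all, BIC chose three or four classes in 12 of 12 replicates. So the simulation in step 1 does not show that mode would be the main source of classes. Step 3 shows only that mode would influence membership.

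**Conclusion.** The point holds in a limited form. The class-forming model in section 6.3.1 (Secondary Outcome) has no term for mode or hospital and no rule for combining modes, and the mixed models do not assure one. Whether this matters depends on an offset that the documents do not give. Under the stated assumptions, offsets of 4 points or more that are constant can produce a false level class even with 10% of children affected. Lasting switches of 4 points can produce a false decline class with 30% affected, but did not with 10%. Two-point offsets rarely produce either. The documents do not support a claim that modes will be pooled, that false recovery patterns are likely, or that the bacteremia estimate is biased as planned.

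The matter is minor. It concerns one secondary objective and leaves both primary endpoints untouched. It is still worth acting on, because the relapse and survival comparisons rest on these classes and the handling is best fixed before any classes are seen.

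**What to change.** In section 6.3.1 (Analysis of Secondary Outcome of Interest):

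1. Include measurement mode as a time-varying covariate, with a category for undocumented mode, in the class-forming trajectory model and in the mixed models.
2. Include hospital in both model types, to cover differences between hospitals within a mode.
3. Add one sensitivity analysis restricted to a single prespecified mode across all children. Restricting to each child's own most frequent mode would not serve, because different children would remain on different modes and a constant offset between them would stay.
4. Report the model without mode adjustment alongside the adjusted one.

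The change is to SAP wording and uses items already listed for abstraction. The costs are small but not nil. The sensitivity analysis uses fewer echocardiograms, and mode may be missing in older charts. If the choice of mode follows severity of illness, adjustment could absorb some true decline in function, which is why the unadjusted result should be shown as well.
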